## 8. STATISTICAL METHODOLOGY AND STATISTICAL ANALYSES

### 8.1. Statistical Methods

#### 8.1.1. Analyses for Continuous Data

All continuous data will be summarized with descriptive statistics, including mean, standard deviation, median, IQR, range and 95% confidence intervals. In addition, change from baseline statistics will be presented as appropriate, to include the appropriate descriptive statistics. For analysis of change from baseline, baseline data from protocol Fx1B-201 will be used as baseline for these analyses. For the change from baseline statistics, the estimate will be adjusted for baseline and the LSMean and standard error will be presented with the 95% confidence interval based on an MMRM model with a random effect for subject and covariate of baseline.

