Following 12 months treatment with tafamidis, along with routine standard of care, 2/35 (5.7%) patients died, 9/35 (25.7%) experienced at least one cardiovascular hospitalization, and 9/35 (25.7%) experienced the composite endpoint of death or cardiovascular hospitalization. Results were similar between the TTR genotype groups. These data were numerically better than that reported in the TRACS historical control cohort, during which the 12-month rate of death, cardiovascular hospitalizations and death/cardiovascular hospitalizations were 6/29 (20.7%), 10/29 (34.5%) and 13/29 (44.8%), respectively.

Cardiac biomarkers (NT-proBNP, troponin I and T) at baseline were elevated, which was not unexpected given the patients' underlying cardiac involvement. The change in NT-proBNP over 12 months was relatively small, and numerically lower than that observed in TRACS. Troponin I and T, more specific markers of cardiac necrosis, remained stable, suggesting no substantial deterioration of cardiac status over 12 months of tafamidis treatment. These data are supported by the functional assessments of NYHA classification and 6MWT. At 12 months, 75% of the patients had improved or preserved NYHA classification, with the overall population demonstrating minimal change in distance walked (-11 meters). This maintained functional walking capacity is in contrast to the deterioration observed in TRACS at 12 months (-44 meters).

Non-invasive cardiac assessments demonstrated significant cardiac involvement at baseline, with substantial ventricular wall thickening (echocardiography and cardiac MRI) and elevated intra-cardiac filling pressures (echocardiography). There were no consistent clinically relevant changes in these parameters over time (echocardiography). For the wild-type patients (the majority of patients in the study), the deterioration in ejection fraction (-3.9) and stroke volume (-8.0) observed in the current study was less than that observed in TRACS (-10.5 and -15.4, respectively) at 12 months. Similar findings were observed in a subset of patients that underwent cardiac MRI. An additional finding in cardiac MRI was a decrease in percent of left ventricle (LV) mass with amyloid observed at 12 months in the small subgroup of patients undergoing this assessment, while there was an increase in LV mass with amyloid observed in TRACS.

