9.2.4. Kansas City Cardiomyopathy Questionnaire

The Kansas City Cardiomyopathy Questionnaire (KCCQ, [Appendix 3](#)) will be summarized by the following summary scores calculated using the guidelines established in the KCCQ Scoring Instruction Manual:

Physical limitations	Self-efficacy
Symptom stability	Quality of life
Symptom frequency	Social limitation
Symptom burden	Overall summary score
Total symptom score	Clinical summary score

Change from baseline for each summary score of the KCCQ will be analyzed using a mixed model analysis (with baseline value as covariate, subjects as random effect, and time as fixed effect). Data will also be summarized by each scheduled assessment and a graphical presentation of these data will be presented.

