### **6.6. Covariates**

Due to the small number of subjects, lack of comparator group and the descriptive nature of this study, baseline will be used as a covariate in the change from baseline models and where appropriate, duration of disease will be used as a covariate.

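### The single-arm change-from-baseline interval leaves out sampling variation in baseline, and the SAP does not say at which baseline value the LSMean is evaluated

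*SAP*

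**What the plan says.** SAP 8.1.1 sets the model for change from baseline: "For the change from baseline statistics, the estimate will be adjusted for baseline and the LSMean and standard error will be presented", with a 95% confidence interval "based on an MMRM model with a random effect for subject and covariate of baseline". The baseline is that of Fx1B-201. SAP 8.2 sends KCCQ, 6-minute walk distance, echocardiography, the troponins and NT-proBNP through this method.

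SAP 6.6 repeats that "baseline will be used as a covariate in the change from baseline models" and adds that "where appropriate, duration of disease will be used as a covariate". Protocol 9.2.4 gives a similar model for KCCQ, "with baseline value as covariate, subjects as random effect, and time as fixed effect".

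Neither document states the baseline value at which the LSMean is evaluated, whether that value is averaged over subjects or over visit records, or whether the standard error allows for baseline being a sampled quantity.

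SAP 8.1.1 also plans unadjusted summaries: "All continuous data will be summarized with descriptive statistics, including mean, standard deviation, median, IQR, range and 95% confidence intervals". Descriptive statistics for change are to be added where appropriate. Protocol 3.1 confirms that there is no control group, and SAP 4.1 that no hypotheses are tested.

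**The concern.** In a two-arm trial, baseline adjustment sharpens the difference between arms. The two LSMeans share one baseline value, so uncertainty about the mean baseline cancels. Here there is no second arm. The LSMean is the result, and the uncertainty stays in it.

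The usual model standard error does not include that uncertainty, so it understates how far the mean change would vary in another sample of TTR-CM patients. That wider reading is a natural one. SAP 4.2 makes 95% intervals the main form of result, and SAP 3.2 foresees reporting at meetings, in publications and to regulators. Protocol 1.2.4 already sets the parent study's walk-test change of -11 m against -44 m in an external cohort.

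The second issue is where the LSMean is evaluated. Follow-up runs for up to 10 years in a disease with a median survival of about 60 months (Protocol 1.2.2), and visits after discontinuation stay missing (SAP 7). Subjects will therefore contribute very different numbers of visit records. If baseline is averaged over records, those with long follow-up count more.

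**Working it through.** The documents give no SD, correlation or interval width for these endpoints, so there is no figure of the plan's own to reproduce.

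**Inputs from the documents:** up to 35 subjects (Protocol 9.1); 2 deaths in the parent study (Protocol 1.2.4), so n = 33 is used; clinic visits every 6 months for up to 10 years; median survival about 60 months.

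**Assumed:** baseline-to-visit correlation r; equal SDs at baseline and visit unless stated; exponential dropout with a 60-month median after month 12; the link between baseline and dropout; a random-intercept model with visit as a fixed effect.

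**Step 1: the missing term.** Let b be the slope of change on baseline and s² the variance of baseline.

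- True variance of the mean change = (residual variance + b² × s²) / n.
- Model-based variance at the mean baseline = residual variance / n.
- Ratio of standard errors = √(1 − ρ²), where ρ is the correlation of change with baseline.

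With equal SDs, b = r − 1. In units of s², the residual variance is 1 − r² and the total is 2(1 − r). The ratio is therefore √((1 + r)/2), and large-sample coverage is 2Φ(1.96 × ratio) − 1.

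| r | SE ratio | Coverage |
|---|---|---|
| 0.9 | 0.975 | 94.4% |
| 0.8 | 0.949 | 93.7% |
| 0.7 | 0.922 | 92.9% |
| 0.5 | 0.866 | 91.0% |

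Example with n = 33 and r = 0.7: the model SE is √0.51/√33 = 0.124 baseline SD, and the full SE is √0.60/√33 = 0.135 SD.

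The SE is 10% too small when |ρ| = √(1 − 0.9²) ≈ 0.44, and not too small at all when ρ = 0.

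**Step 2: unequal SDs.** If the follow-up SD is k times the baseline SD, then b = rk − 1, the residual variance is k²(1 − r²) and the total is k² + 1 − 2rk. For k = 1.2:

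- r = 0.5: √(1.08/1.24) = 0.93.
- r = 0.7: √(0.734/0.760) = 0.98.
- r = 0.8: b = −0.04, and the ratio is practically 1.00.

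The shortfall can therefore be negligible.

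**Step 3: with dropout.** The model was simulated with n = 33, 1,500 runs per setting and variance components treated as known. The hazard of leaving was 1, 1.5 or 2 times as high per SD of lower baseline. With the LSMean evaluated at the mean of one baseline per subject, coverage at months 12 to 60 was about 0.905–0.935 (r = 0.5), 0.93–0.95 (r = 0.7) and 0.935–0.957 (r = 0.85).

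**Step 4: evaluation point.** An LSMean taken at a baseline d SDs above the subject mean moves by b × d. If baseline is averaged over visit records:

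- Hazard ratio 1: d is about 0, so there is no bias.
- Hazard ratio 1.5: d ≈ 0.21. The longest-followed quarter of subjects lies at about 0.44.
- Hazard ratio 2: d ≈ 0.33. The longest-followed quarter lies at about 0.64.

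The evaluation point thus moves about half way towards the longest-followed quarter. At hazard ratio 2, b × d = −0.5 × 0.33 ≈ −0.16 SD for r = 0.5, −0.10 SD for r = 0.7 and −0.05 SD for r = 0.85. The simulation gave the same values. Coverage was then 0.78–0.86, 0.86–0.91 and 0.91–0.93 respectively.

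**Step 5: the fix.** With one baseline per subject as the evaluation point and b² × s² / n added to the squared SE, coverage was 0.94–0.96 in all nine settings and bias was within 0.012 SD.

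**The case against.** The case for leaving the plan alone has real substance.

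- The interval is valid conditional on the enrolled subjects' baselines. This is a fixed cohort of completers of one earlier study, no hypothesis is tested, and no decision rule depends on these intervals. This stands, and it limits the consequence. It does not cover the natural wider reading, and the SAP does not tell the reader that the interval is conditional.
- Unadjusted summaries are also planned, and Protocol 9.2.5 and 9.2.7 ask only for descriptive statistics for the walk test and the biomarkers. This stands too. But those summaries use only subjects still observed at each visit (SAP 7), so they do not replace a model that uses every subject's data.
- Treating baseline as a covariate is a recognised choice. It is, and the second remedy below keeps it.

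A reader might infer more: that the LSMean is set at the baseline of the longest-followed subjects, that both effects arise at every visit whatever the data, or that coverage near 80% is what the plan delivers. The documents do not support this. They state no evaluation point, and averaging over records is an assumed software default. If rows for missed visits are kept and counted in that average, each subject has equal weight and the tilt disappears. Even with record averaging, the value moves only part of the way, and there is no bias unless baseline predicts length of follow-up. Some subjects will leave because prescription drug becomes available (Protocol 6.3), a reason not obviously tied to baseline. The lowest coverage figures combine a weak correlation with a strong assumed link to dropout. No walk-test SD is given, so the shift cannot be put in metres and set against the -11 m.

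**Conclusion.** The point holds in a limited form. As an interval for mean change in the patient population, the planned interval is too narrow whenever change is correlated with baseline. With equal SDs and complete data the shortfall is about 2% to 13% for r from 0.9 to 0.5 (coverage about 94% to 91%). It is close to nil if change is uncorrelated with baseline, as can happen when the spread grows over time. The missing term follows from algebra. Its size rests on a correlation that the documents do not give. The same reasoning applies to disease duration where that is used as a covariate.

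The unstated evaluation point is a gap in specification, not a stated rule that is wrong. Its effect depends on two assumptions: averaging baseline over records, and a link between baseline and length of follow-up.

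The consequence is modest in a descriptive study, but the change is worth making before these intervals are reported.

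**What to change.** Change SAP 8.1.1 and 6.6, and align Protocol 9.2.4, in one of two ways.

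1. Enter the Fx1B-201 baseline as the first repeated response, with visit as a fixed effect, and drop it as a covariate. Report change as the visit mean minus the baseline mean, with the standard error of that contrast. Baseline still informs the handling of dropout.
2. Keep the covariate. State that every LSMean is evaluated at the mean Fx1B-201 baseline with one value per analysed subject, and add slope² × SD_baseline² / n to the squared standard error.

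The cost is SAP wording and a few lines of code, with no new data. The drawback is wider intervals: with complete data and equal SDs, about 3% wider at r = 0.9 (1/0.975) and 15% wider at r = 0.5 (1/0.866).

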#### 8.1.2. Analyses for Categorical Data

All categorical data will be summarized as n, percentage and 95% confidence intervals. The 95% CI intervals will be estimated using exact methods due to the decreasing sample size. In addition, a shift table will be provided for such variables as the 6 minute walk test, PGA, and NYHA class.

#### 8.1.3. Analyses for Time to Event Endpoints

Kaplan-Meier estimates will be computed for all time to event endpoints, including median and interquartile ranges, where appropriate. 95% confidence intervals will be presented at yearly intervals from the start of the investigational drug (baseline of Fx1B-201). Time to event will use randomization and onset of disease as starting points for the calculation of time to event.

Subjects are required to survive to enroll in the parent study (Fx1B-201). Such conditions yield a left-truncated death time distribution from symptom onset. To account for the potential immortal time bias, the time to death from onset of symptom will be analyzed using the delayed entry (left truncation) technique. Survival probabilities will be calculated conditional on subjects having survived until study entry of the parent study (Fx1B-201). SAS codes for the delayed entry (left truncation) technique are provided in Appendix 5.

## 8.2. Efficacy Analyses

Efficacy analyses will be performed for cumulative efficacy data as measured by Patient Global Assessment (PGA), New York Heart Association (NYHA) classification, Kansas City Cardiomyopathy Questionnaire (KCCQ), 6-minute walk test (6MWT), echocardiograms, and serum levels of troponin I, troponin T, and NT-proBNP.

The analyses will use the methods described above for these continuous outcomes in [Section 8.1.1](#):

- Kansas City Cardiomyopathy Questionnaire (KCCQ)
- 6-minute walk test (6MWT)
- Echocardiograms
- Serum levels of troponin I, troponin T, and NT-proBNP.

The analyses will use the methods described above for these categorical outcomes in [Section 8.1.2](#):

- Patient Global Assessment (PGA)
- New York Heart Association (NYHA) classification
- 6-minute walk test (6MWT) (categorized by level as described below)

Shift tables will be provided for the following variables:

- Patient Global Assessment (PGA)
- New York Heart Association (NYHA) classification
- 6-minute walk test (6MWT) (categorized as stable, improved, worsened)

## 8.3. Safety Analyses

Safety data will be summarized for the safety analysis population.

**Treatment and Disposition of Subjects:** Subject evaluation groups will show end of study subject disposition and will show which subjects were analyzed for efficacy, as well as for

safety (adverse events and laboratory data). Frequency counts will be supplied for subject discontinuation(s) by treatment.

A listing of treatment duration for each subject will be reported in accordance with the sponsor reporting standards.

**Demographic and Baseline Characteristics.** A break-down of demographic data will be provided for age, race, weight, body mass index, and height. Each will be summarized by sex at birth and ‘All Subjects’ in accordance with the sponsor reporting standards. All baseline and disease characteristics will also be summarized for Fx1B-201 and B3461026, respectively.

**Discontinuations.** Subject discontinuations or temporary discontinuations due to adverse events will be detailed and summarized.

**Adverse events (AEs):** Adverse events will be summarized by causality and severity.

**Mortality and Hospitalization (all-cause and cardiac-related):** Time to all-cause mortality and time to cardiac-related mortality will be calculated from the first dose of the randomized treatment in Study Fx1B-201, and from onset of symptom, respectively. For cardiac-related mortality, subjects who died for reasons other than cardiovascular will be designated as censored at the time of death. Subjects alive at the end of the study will be censored at the last visit date. Death after discontinuation will be censored at time of discontinuation. For subjects who have received a liver and/or heart transplant, time will be censored at the time of transplant. The analyses will use the methods described for time to event endpoints in [Section 8.1.3](#). The analyses will be performed on the safety analysis population (defined in [Section 5.1](#)).

The number and percentage of subjects hospitalized (all-cause and cardiac-related) during the study will be summarized descriptively.

**Hematology, Biochemistry and Urinalysis:** Descriptive statistics will be provided for each test result and for change from baseline by visit.

Baseline is defined as the last evaluation prior to the first dose of study drug in Study Fx1B-201.

**Cardiac Measures:** Changes from baseline (defined as the last evaluation prior to the first dose of study drug) will be summarized for each of the cardiac parameters listed above by visit. Clinically significant changes in ECG measures (as indicated by the items in [Section 6.2, #6](#), item h through m) at any point during the study will be summarized.

Pacemaker and defibrillator insertion procedures will be identified through a programmatic search of potentially related terms in the clinical database coupled with a manual review by Pfizer Clinical.

The following MedDRA Lower Level Terms (codes) will be applied to the Medical History, Adverse Events, and Investigator Comments to identify potential procedures in the clinical

database: CARDIOVERTER PLACEMENT (10053015), INSERTION OF IMPLANTABLE CARDIOVERTER DEVICE (10052044), CARDIAC PACEMAKER INSERTION (10007598), PACEMAKER INSERTION (CARDIAC) (10033352), DEFIBRILLATOR/PACEMAKER INSERTION (10069072), IMPLANTABLE DEFIBRILLATOR INSERTION (10049442).

The following terms will also be searched to identify potential associated procedures collected in the Investigator Comments CRF: pacemaker, implantable cardiac device, ICD, AICD, cardioversion, cardioverter, defibrillator, ventricular fibrillation, ventricular tachycardia.

Final search criteria and categorization of pacemaker and defibrillator will be based on the results of the clinical review and will be described in the programming plan prior to database finalization.

The number and percentage of subjects with pacemaker or defibrillator insertion procedures (defined above) will be summarized by category and for overall at baseline of Fx1B-201, the number and percentage of subjects who have such devices implanted during the course of Fx1B-201 and during the course of B3461026 (Fx1B-303), respectively.

**Vital signs:** Will be summarized using descriptive statistics, to include: values at each visit, change from baseline to each visit and a categorization of clinically significant changes.

Significant changes from baseline are defined as follows:

- Systolic Blood Pressure (mmHg) Decrease (Change  $\leq$  -20, or Value < 90)
- Systolic Blood Pressure (mmHg) Increase (Change  $\geq$  20, or Value > 180)
- Diastolic Blood Pressure (mmHg) Decrease (Change  $\leq$  -15, or Value < 50)
- Diastolic Blood Pressure (mmHg) Increase (Change  $\geq$  15, or Value > 105)
- Heart Rate (bpm) Decrease (Change  $\leq$  -15, or Value < 50)
- Heart Rate (bpm) Increase (Change  $\geq$  15, or Value > 120)
- Weight (kg) Decrease (Change  $\leq$  -7%)
- Weight (kg) Increase (Change  $\geq$  7%)

Orthostatic hypotension is present under any of the following conditions:

- (Lying Systolic Blood Pressure - Standing Systolic Blood Pressure)  $\geq$  20 mmHg, or
- (Lying Diastolic Blood Pressure - Standing Diastolic Blood Pressure)  $\geq$  10 mmHg, or
- (Standing Pulse - Lying Pulse)  $>$  20 bpm along with (Standing Pulse or Lying Pulse  $>$  100bpm)

If pulse is missing at any visit, then evaluate orthostatic hypotension using only blood pressure measures.

**Concomitant medications:** will be summarized.

**Physical Examination and Medical History:** Results will be summarized and listed.

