1.2.2. Study Rationale

The initial development activities for tafamidis were undertaken in patients with TTR-FAP. Safety data in this population, and the results from the TRACS study, led to the initiation of Protocol Fx1B-201, a 12-month trial of tafamidis in patients with TTR-CM. The results of the Fx1B-201 study will be used in the design of a Phase 3 program that will evaluate the efficacy and safety of tafamidis in TTR-CM.

TTR-CM is a slowly progressing disease with a median survival of approximately 60 months [14, 15]. It is currently not known whether tafamidis will be effective in slowing or halting the progression of TTR amyloid cardiomyopathy, or when such an impact would become evident. Therefore, the purpose of the current study is to assess the long-term safety and

efficacy of tafamidis in patients with ATTR-CM. Eligible patients who successfully completed Protocol Fx1B-201, having received open-label tafamidis for 12 months, may enroll in Protocol Fx1B-303 and continue to receive open-label tafamidis for up to an additional 10 years.

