4.2. Exclusion Criteria

Subjects presenting with any of the following will not be included in the study:

1. Subject has not successfully completed Protocol Fx1B-201.
2. Chronic use of non-protocol approved non-steroidal anti-inflammatory drugs (NSAIDs), defined as greater than 3 to 4 times/month. The following NSAIDs are allowed: acetylsalicylic acid, etodolac, ibuprofen, indomethacin, ketoprofen, nabumetone, naproxen, nimesulide, piroxicam, and sulindac.
3. Subject has a clinically significant medical condition that, in the opinion of the Investigator, would place the subject at an increased risk to participate in the study.
4. Pregnant females; breastfeeding females; females of childbearing potential.
5. Subject has received a liver or heart transplant.

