9.2.8. Mortality and Hospitalization

The endpoints of mortality and hospitalization (all cause and cardiac-related) will be analyzed individually and as composite measures.

A Kaplan-Meier plot of time to event from the start of Protocol Fx1B-201 will be generated, and the event rate and associated 95% confidence intervals will be presented at 1, 2, 3, and 4 years since the start of the investigational drug.

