## **5. ANALYSIS SETS**

### **5.1. Safety Analysis Population**

The safety analysis population consists of all subjects who are enrolled in this study and who have taken at least one dose of study medication.

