**8. Mortality and hospitalization (all-cause and cardiac-related)**

All-cause of mortality is defined as any death occurring during the study. Cardiac-related mortality will be any mortality meeting the following MedDRA criterion: 1) AE body system (AEBODSYS) = "CARDIAC DISORDERS", or 2) AE preferred term (AEDECOD) in (CHEST DISCOMFORT, CHEST PAIN, DEATH, CEREBROVASCULAR ACCIDENT, EMBOLIC STROKE, DISEASE

PROGRESSION). Description on the time to mortality analysis can be found in [Section 8.1.3](#).

All cause of hospitalization is defined as any adverse event for which SAE type “3=Hospitalization” in the Adverse Event (AE) CRF. The cardiac-related hospitalization will be any hospitalization meeting the following MedDRA criterion:1) AE body system (AEBODSYS) = “CARDIAC DISORDERS”, or 2) AE preferred term (AEDECOD ) in (CHEST DISCOMFORT, CHEST PAIN, DEATH, CEREBROVASCULAR ACCIDENT, EMBOLIC STROKE, DISEASE PROGRESSION).

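### Mortality is timed from first dose in Fx1B-201 but analysed only in subjects who completed that 12-month study, so year-1 survival is about 100% by eligibility and later survival is conditional without being labelled so

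*SAP*

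**What the plan says.** **Clock.** SAP 8.3: "Time to all-cause mortality and time to cardiac-related mortality will be calculated from the first dose of the randomized treatment in Study Fx1B-201". The same section plans a second analysis from symptom onset.

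**Analysis set.** SAP 8.3 continues: "The analyses will be performed on the safety analysis population". SAP 5.1 defines that set as "all subjects who are enrolled in this study and who have taken at least one dose" of study medication, and this study is Fx1B-303.

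**Deaths counted.** SAP 6.2 item 8: "All-cause of mortality is defined as any death occurring during the study".

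**Who can enter.** Protocol 4.2 excludes anyone to whom this applies: "Subject has not successfully completed Protocol Fx1B-201". Protocol 1.2.2 describes the eligible subjects as "having received open-label tafamidis for 12 months, may enroll in Protocol Fx1B-303".

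**What is reported.** Protocol 9.2.8 starts the Kaplan-Meier plot at the start of Fx1B-201 and says that the "event rate and associated 95% confidence intervals will be presented at 1, 2, 3, and 4 years" after the start of drug. SAP 8.1.3 also asks for yearly intervals from the Fx1B-201 baseline.

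**Immortal-time correction.** SAP 8.1.3 uses delayed entry for time from symptom onset only: "Survival probabilities will be calculated conditional on subjects having survived until study entry of the parent study (Fx1B-201"). In Appendix 4 the entry variable `los` runs from symptom onset to the start of Fx1B-201.

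**The concern.** The clock starts about a year before a subject can join the analysis set, and joining requires being alive at the end of that year. Those months are immortal time: they count as follow-up, but no death in them can be recorded. This has three consequences.

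- The year-1 survival estimate reflects the entry criteria and says nothing about the drug or the disease.
- Later values estimate survival given completion of Fx1B-201 and entry to Fx1B-303. The plan presents them as survival from first dose without that condition.
- On the onset scale the SAP sets out to remove immortal time, but it conditions on survival to the start of Fx1B-201. The condition that its analysis set actually meets is survival to Fx1B-303 entry. About 12 death-free months per subject stay in the risk set.

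Long-term data are the first objective of this single-arm extension, and SAP 3.2 intends interim results for scientific meetings, publication and regulatory use. Protocol 1.2.4 already sets 12-month mortality in Fx1B-201 beside the TRACS historical cohort, 2/35 against 6/29 (20.7%). A year-1 mortality of about 0% would flatter any such comparison.

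**Working it through.** **Inputs.** From Protocol 1.2.4: 35 subjects treated in Fx1B-201, 2 deaths over 12 months, disease duration about 8 years. From Protocol 1.2.2: Fx1B-201 lasts 12 months, and median survival is about 60 months. The number who entered Fx1B-303 is not given; Protocol 9.1 says up to 35.

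**The plan's own figure.** 2/35 = 5.7%, as stated, so 33/35 = 94.3% were alive at 12 months. The exact (Clopper-Pearson) 95% CI for 2/35 is 0.70% to 19.16%, which gives survival of 80.8% to 99.3%.

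**Year 1 as planned.** Everyone in the set was alive at about month 12, so the estimate is about 100% with zero Greenwood variance. It is only about 100% because a subject could have entered Fx1B-303 a few days before day 365.

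**Later years, first-dose scale.** For t of at least 12 months,

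S_all(t) = S(12 months) × S(t | alive at 12 months).

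The planned curve estimates only the second factor. The ratio of planned to all-treated survival is 1/S(12 months) = 35/33 = 1.061. The exact limits give 1/(1 − 0.0070) = 1.007 to 1/(1 − 0.1916) = 1.237. A simulation of 35 subjects at the parent-study hazard gave a ratio of 1.061 at each of years 1 to 4.

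**Illustration.** Assume a constant hazard h after year 1. The planned value is exp(−h(t − 1)), and the all-treated value is that × 33/35.

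| Year | Planned, h = ln2/5 = 0.1386 | All treated | Planned, h = −ln(33/35) = 0.0588 | All treated |
|---|---|---|---|---|
| 1 | 100% | 94.3% | 100% | 94.3% |
| 2 | 87.1% | 82.1% | 94.3% | 88.9% |
| 3 | 75.8% | 71.5% | 88.9% | 83.8% |
| 4 | 66.0% | 62.2% | 83.8% | 79.0% |

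With h = ln2/5 the planned median is 12 × (1 + 5) = 72 months. The all-treated median is 12 × (1 + ln((33/35)/0.5)/h) = 66.9 months.

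**Sampling error for scale.** At year 4 with S = 0.66, n = 33 and no censoring, the 95% half-width is 1.96 × √(0.66 × 0.34/33) = 0.16.

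**Onset scale.** The delayed-entry product-limit estimate was simulated with 200,000 subjects per scenario. First-year mortality was set at 2/35 and the later hazard at 0.0588 or 0.1386 per year. Time from onset to Fx1B-201 was gamma with mean 8 years and assumed shape 1, 2, 4 or 8. Follow-up was assumed to be 5, 8 or 11 years. The measure is survival to year 12 after onset given alive at year 6, an illustrative window. The planned set exceeded all dosed subjects, with the same entry point, by 2.2 to 6.5 points at 0.0588 and by 1.9 to 4.9 points at 0.1386. At shape 4, 5-year follow-up and 0.0588, the figures are 75.5% against 70.2%. At that constant hazard, moving entry forward one year removes the excess, which identifies the entry point as the cause.

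**The case against.** **Later values are legitimate conditional survival.** SAP 5.1 and 8.3 name the analysis set, and a careful reader could work out the condition. This stands: after year 1 on the first-dose scale, the fault is that the estimand is not labelled. It does not rescue year 1 or the onset-scale entry time.

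**The 6% is uncertain.** It rests on 2 deaths, and it assumes that survivors who did not enter Fx1B-303 had the same later survival as those who did. At a planned value of 70%, if 2 to 6 survivors did not enter and had half that survival, the inflation would be 9% to 17%. If their survival was 15% better, it would be 3% to 5%. The direction stays the same in all of these cases. Sampling error at year 4 is also larger than the bias, but that does not justify keeping a bias that can be removed.

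**The onset-scale size depends on assumptions.** This also stands. The 6-to-12-year window was chosen for illustration and is not a planned output. Early risk sets are very small, so differences over the full curve can be much larger. The range shows direction and order of size only.

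**Hospitalisation.** Immortal time in the strict sense concerns death only, but the same selection touches hospitalisation. In Protocol 1.2.4, cardiovascular hospitalisation and death-or-hospitalisation are both 9/35, so both subjects who died had been hospitalised. Removing them turns 9/35 (25.7%) into 7/33 (21.2%) for each measure.

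**The study is descriptive, and the protocol reports the 2/35.** This is true and limits the severity. An estimate fixed by eligibility is still not a useful description.

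**Conclusion.** The concern holds, and the plan should be changed. The clock and the analysis set do not match, and nothing elsewhere in either document repairs this. Year-1 survival is affected most: about 100% by eligibility against 94.3% observed. Later first-dose values need a conditional label. Taken as survival of all treated subjects, they are about 6% too high in relative terms (0.7% to 23.7% from the exact interval), or at most 5.7 points on the observed data. That size takes 2/35 as the 12-month Kaplan-Meier value and assumes non-informative censoring of living non-enrollers at month 12. On the onset scale the entry time is wrong for the set analysed and survival is overestimated, by roughly 2 to 6.5 points in the scenarios tried. Confidence is high on the mismatch and its direction, and lower on the exact size.

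**What to change.** **Preferred.** Add to SAP Section 5 a mortality analysis set of all 35 subjects dosed in Fx1B-201. Extend SAP 6.2 item 8 so that deaths in Fx1B-201 count. Censor living non-enrollers at their last Fx1B-201 contact, and report how many there were. Name this set in SAP 8.3 for both time scales. The existing `los` is then correct, and the year-1 rate in Protocol 9.2.8 can stay.

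**Alternative.** Keep the Fx1B-303 safety population and use delayed entry at Fx1B-303 Day 1 on both scales. Entry is then the time from Fx1B-201 first dose to Fx1B-303 Day 1 on the first-dose scale, and from onset to Fx1B-303 Day 1 on the onset scale. Label every mortality estimate as conditional on completing Fx1B-201 and entering Fx1B-303. Omit the year-1 mortality rate and record this as a departure from Protocol 9.2.8. On the first-dose scale this changes the label and the year-1 figure, not the later values.

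The two options answer different questions and can differ on the onset scale. At shape 4, 8-year follow-up and hazard 0.1386, survival from year 6 to year 12 was about 51.5% as planned, 48% under the preferred option and 44% under the alternative. The SAP should choose one in advance. Under either option, hospitalisation and composite rates reported for the Fx1B-303 set from Fx1B-201 first dose should carry the same conditional label.

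**Cost.** SAP wording in Sections 5, 6.2, 8.1.3 and 8.3, Appendix 4 code for the alternative, and some programming. No new data collection is needed, since the Fx1B-201 outcomes already exist; the preferred option does require bringing in records of subjects who never entered Fx1B-303. The survival figures become slightly less favourable.
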